Challenge 1. There is variability in the type and frequency of EPI services offered. Variability was particularly noted in aspects of recovery-oriented care, including comprehensive care planning and monitoring, use of psychotherapies (CBT), family support, and employment support. A lack of protocols to guide such delivery and inconsistent documentation was a common theme.

Challenge 2. Programs expressed a need for more tools and protocols to guide service delivery, more consistent access to training, and lack of time for training in the implementation of new practices.

Challenge 3. Programs desired opportunities to learn from peers in a community of practice, and noted resource challenges such as accessing expertise and travel time.

How Will this Study Address the Identified Challenges?

We want to address these challenges in Ontario EPI settings by implementing NAVIGATE, a coordinated and comprehensive multidisciplinary treatment program for FEP that is deliverable in community mental health settings. NAVIGATE is manualized and measurement-based. To maximize affordability, adaptability, spread, and sustainability, the key elements of success for an implementation project as defined by CIHR, we will utilize a) the already-established EPION community of practice, b) the implementation science expertise of PSSP, and c) the sustainability and capacity building approach of The Extension of Community Health Outcomes (ECHO) Ontario Mental Health at CAMH and the University of Toronto (ECHO-ONMH). These are detailed point-by-point below. We first briefly explain, and summarize the evidence for NAVIGATE.

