Challenge 1. Need to Standardize Care, Particularly Recovery-Oriented Care and Manualized Protocols: NAVIGATE operationalizes current EPI standards using manualized protocols, ensuring consistency and reducing variability in care. The four NAVIGATE components (individualized medication management, IRT, SEE, and family education program) are systematically applied in collaboration with the patient³³. There is an overarching emphasis on the coordinated delivery of these elements of care. Every patient is offered these elements of care, and modules are completed in a systematic time-oriented fashion

that reduces variability in care among sites and team-members within a site. For instance, goal-setting and identification of personal strengths are consistently discussed at the first visit. This ensures that care is systematically oriented and aligned towards patient preference. At each patient visit, a contact/progress note is completed, including the modules delivered, that the team reviews to assess patient progress, fidelity, and determine need for adjustments.

Challenge 2. Need for Consistent Access to Training, To Investigate and Implement New Practices:

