3.1. Primary Objectives

1. Assess whether implementation of NAVIGATE leads to improvement in fidelity to the EPI standard (using the FEPS-FS).
2. Compare system-level outcomes, i.e. days in hospital, emergency department visits, suicide attempts, mortality, and system costs among patients receiving NAVIGATE compared with patients at other EPI sites not receiving NAVIGATE and patients with psychotic disorders who are not enrolled in EPI.
3. Determine longitudinal change in functioning and symptoms in NAVIGATE patients.
4. Evaluate patient and family member engagement according to the SPOR framework.

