Proctor's implementation outcomes⁶¹ will guide evaluation of implementation outcomes: three of the four CIHR implementation science metrics (adaptability, scalability, sustainability). Specifically we will assess i) fidelity (i.e. adaptability) to examine the extent to which programs operating in different contexts with different resources are able to implement NAVIGATE as intended. Second we will assess ii) penetration (i.e. scalability) the extent to which all eligible program patients receive NAVIGATE. Using the Consolidated Framework for Implementation Research (CFIR)⁶², we will assess contextual factors (stakeholder perceptions of acceptability, appropriateness, feasibility) that help or hinder use of NAVIGATE. Learning about these factors including how they relate to unique aspects across settings will inform wider efforts to adapt NAVIGATE and tailor implementation (adaptability and scalability). We will also assess iii) sustainability through uptake of the ECHO model. We address the fourth CIHR implementation science metric (affordability) in the System-Level outcome section further below.

i) Fidelity (ADAPTABILITY): We will use the First Episode Psychosis Service–Fidelity Scale (FEPS-FS)²⁹ to assess fidelity of service delivery to the current standard of EPI evidence-based practice in relation to 31 program-specific items (individual and team practices) on a 5-point scale from “not implemented” to “fully implemented”. Ratings for each site will be made by centrally located trained assessors through a remote assessment process that includes a review of site administrative data, data abstracted from client health records by trained abstractors, and phone interviews with site staff. The FEPS-FS was developed with a formal knowledge synthesis process rather than a single program model. It was used in the Ontario pilot and is relevant to the Ontario EPI standards. Reviews will be conducted at three points in time: during the exploration stage, after full implementation is reached and at the study end to assess sustainability. To examine fidelity results, site will be the unit of analysis. Descriptive statistics (percentages, means, medians, range) will be reported for the total scale score and for subscale scores that align with NAVIGATE

components. With a small number of sites, we cannot quantitatively test changes over time and across sites, but will describe and qualitatively compare findings.

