For additional validation of intervention delivery, fidelity scores will be calculated per site in relation to the four core NAVIGATE interventions (medication, IRT, SEE, family education) using the service utilization measure (see description in previous section). The Clinician Contact and Progress Note (a standard documentation template within NAVIGATE for IRT, SEE, and FEP components of treatment, captured in client health records, which captures information about which module was covered during each treatment session) will provide model adherence data for each patient across the core interventions. This will be augmented by the Service Use and Resource Form (SURF) that research staff will complete with each patient. We will mirror the original study, calculating the percentage of core modules completed per intervention per patient.

ii.a.) Penetration (SCALABILITY): Penetration assesses the extent to which eligible program patients receive the NAVIGATE treatments, and identifies any biases in delivery^{61,63}. This is important because a core aim of NAVIGATE is to increase consistency of model delivery across in patients across all programs. Fidelity to NAVIGATE will be calculated from the contact forms (clinician report) and the SURF (client report), and will be used to assess penetration and to identify variations in delivery across patients within sites and across sites. When assessing scalability, the unit of analysis will be the patient (n=400 patients). The outcome will be percentage of modules received for each of the four interventions and will be reported using percentages, means, medians, standard deviations, and interquartile ranges. A linear regression model will be used to identify predictors, with patient baseline characteristics such as sex, age, and illness complexity. The nesting of patients within each site will be accounted for in the analysis. All statistical tests will be two-tailed and statistical significance will be defined as p-values less than 0.05.

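### Part of any rise in FEPS-FS after NAVIGATE may reflect better charting, because the program adds a structured note to a record used for the ratings

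*Combined protocol and SAP*

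**What the plan says.** Section 3.1 lists as its first objective: "Assess whether implementation of NAVIGATE leads to improvement in fidelity to the EPI standard (using the FEPS-FS"). Hypothesis 1 in section 3.2 expects fidelity to improve.

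Section 4, under Evaluation of Implementation outcomes (Objective 1), i) Fidelity, describes the scale as "31 program-specific items (individual and team practices) on a 5-point scale". Central trained assessors rate each site through "a remote assessment process that includes a review of site administrative data", together with "data abstracted from client health records by trained abstractors, and phone interviews with site staff". The reviews take place "during the exploration stage, after full implementation is reached and at the study end to assess sustainability". Results are described with the site as unit and are not tested.

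The same part of section 4 describes the Clinician Contact and Progress Note. It is a standard template for IRT, SEE and a component abbreviated FEP, which I read here as the family education program. It is "captured in client health records, which captures information about which module was covered during each treatment session". Section 2.1 (Need to Standardize Care) adds: "At each patient visit, a contact/progress note is completed, including the modules delivered".

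On the state of the records before NAVIGATE, the first list of challenges in section 2.1 reports: "A lack of protocols to guide such delivery and inconsistent documentation was a common theme". That sentence concerns recovery-oriented care.

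**The concern.** A before-after comparison needs the score to mean the same thing at each review. Here one of the three rating sources is changed by the intervention. If a program delivered family education or employment support at baseline but did not write it down, the baseline chart cannot show it. Once the NAVIGATE note is in use, the same care leaves a dated, structured trace. An assessor following the same instructions could then give a higher rating although care had not changed.

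The stake is the reading of Hypothesis 1. Subscales that align with NAVIGATE are to be reported, and these cover the domains in which the note is kept. With no FEPS-FS at comparison sites and no test of change, interpretation rests on the score itself. Section 7 says that the provincial ministry partner wants to carry findings into policy, so a rise due partly to recording could be read as a rise in care.

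**Working it through.** The documents give no effect size, standard deviation or power for FEPS-FS, so there is no figure to reproduce. The check has two parts.

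**1. Does the timing allow the artefact?** From the table of implementation evaluation measures and timeline in section 4:

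| Measure | Months 1-3 | Months 4-6 | Months 7-12 | Months 13-24 | Months 25-42 |
|---|---|---|---|---|---|
| FEPS-FS | yes | no | no | yes | yes |
| Clinician contact form | no | yes | yes | yes | yes |
| SURF (client report) | no | yes | yes | yes | yes |

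The baseline FEPS-FS review comes before the note; the two later reviews come after it. SURF has no mark in months 1-3, and none at admission in the Schedule of Assessments in section 3.3. It is also not named as a FEPS-FS source. It therefore cannot check a before-after change. The plan states no masking of assessors to time point and no rule for care that was delivered but not recorded.

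**2. How large could it be?** The number of chart-rated items, the gain per item and the completeness of recording are all absent. Everything below is assumed and shows a range only.

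(a) If k of the 31 items each gain g points through recording alone, the mean item score rises by k × g / 31.

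| k (share of items) | g = 0.5 | g = 1 |
|---|---|---|
| 3 (about 10%) | 1.5/31 = 0.05 | 3/31 = 0.10 |
| 8 (about 25%) | 4/31 = 0.13 | 8/31 = 0.26 |
| 16 (about 50%) | 8/31 = 0.26 | 16/31 = 0.52 |
| 23 (about 75%) | 11.5/31 = 0.37 | 23/31 = 0.74 |

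For a subscale of m items, of which c are decided by the chart, the rise is c × g / m. It reaches g only if c = m, that is, if the chart decides every item.

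(b) If true delivery p is constant and recording completeness moves from s0 to s1, the rate seen in the chart moves from p × s0 to p × s1. With p = 50%:

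- s from 90% to 95%: 45.0% to 47.5%, a rise of 2.5 points.
- s from 70% to 95%: 35.0% to 47.5%, a rise of 12.5 points.
- s from 50% to 95%: 25.0% to 47.5%, a rise of 22.5 points.

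(c) Direction. Suppose that a vague chart is sometimes credited for care not given, at rate f. The chart-based rate is then p × s + (1 − p) × f, and its change is p(s1 − s0) + (1 − p)(f1 − f0). A module-by-module note should raise s but may lower f, so the second term can be negative. Given inconsistent records at the start, upward is the likelier net direction, but it is not guaranteed.

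**The case against.** The strongest counter-argument comes from section 2.1 itself. The artefact needs care that was given but not recorded. The team's earlier fidelity study, which used the same scale, reports as its most notable finding that recovery-oriented care was not consistently delivered. That picture was enriched by site visits and in-person interviews, so it was not a chart-only inference. Much of the baseline deficit was probably real. This stands, and it limits how much of a rise should be put down to recording.

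Other points also carry weight:

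- Scale, sources and type of assessor are the same at all reviews. Administrative data and interviews can credit unrecorded care at baseline.
- Section 4 assigns the note to a separate measure of NAVIGATE adherence. Its use as FEPS-FS evidence is inferred from its place in the client record.
- The team uses the note to review progress and adjust care, so better notes may be part of better care.
- Medication is not among the components that the template is said to cover, so medication and team-structure items are less exposed.
- The analysis is descriptive and is read alongside staff interviews and readiness scores.

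These points reduce the concern without removing it. Staff who are interviewed know that NAVIGATE has been introduced. Central assessors cannot see what a baseline chart omits. No planned element separates better notes from better care.

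**Conclusion.** The mechanism is supported by the documents. Part of any rise in FEPS-FS may reflect better recording; the likely direction is upward. The size cannot be determined. The 0.05 to 0.74 points on the mean item score, and the 2.5 to 22.5 percentage points in a chart-based rate, rest wholly on assumed inputs, and the real effect may be negligible.

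A reader might infer three stronger things that the documents do not support:

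- **The score can only move up.** A detailed note can also expose modules that were not delivered.
- **Hypothesis 1 would be met with no change in care.** Section 2.1 points to a real baseline deficit in delivery, which NAVIGATE may well improve.
- **The aligned subscales would rise by half a point to a full point from recording alone.** With those gains per item, this needs nearly every item in them to be decided by the chart, although ratings draw on three sources.

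This is a point about interpreting a primary objective. It is not a numerical error, and it is worth acting on because the remedy is cheap.

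**What to change.** 1. At all three reviews, record for each FEPS-FS item which source supports the rating (chart, administrative data, staff interview) and whether the NAVIGATE note was the sole evidence. Start at the baseline review, because sources may not be recoverable later.
2. Write one rule for care that was delivered but not recorded, and apply it identically at all three reviews; for example, that it may be credited from interview or administrative data.
3. Keep the planned total and subscale scores as the main description. Add a sensitivity description of change with and without items that rest on the chart, and with and without items that rest solely on the NAVIGATE note.
4. State the documentation artefact as a limitation when interpreting Hypothesis 1.

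I would not bar the note as evidence, nor make a claim of improvement depend on items outside it. The note covers IRT, SEE and family education, which NAVIGATE is meant to change, so either step could hide real gains.

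The cost is one extra field on the rating sheet and one abstraction instruction, with no new staff or visits. The sensitivity result may look less favourable. It will not be decisive on its own, because chart-dependent items overlap with those that NAVIGATE targets.

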Although each EPI program has existing processes for providing the components of early psychosis care, these are not necessarily delivered in the systematic and intentional manner outlined through NAVIGATE. Building on a large body of practice change evidence supporting a ‘make it happen’ rather than ‘let it happen’ approach^{34,58}, we will guide each program site through a facilitated, staged, change process informed by the Active Implementation Framework and the Quality Implementation Framework^{34,59}. A regional PSSP facilitator will have primary responsibility for the implementation, working closely with the CAMH NAVIGATE experts, and EPI program staff lead at each site. The CAMH NAVIGATE experts and PSSP facilitator will bring expertise and momentum to the work. The PSSP facilitator, EPI program staff lead, and ECHO team will assist with site engagement, understanding and preparing the program context, and local problem-solving⁶⁰.

Although sites will vary somewhat in their pace of implementation, we expect that installation (see below) will occur across the first six months, that trialing and refining will occur during months 7-12, and that practice will become embedded after month 12. Thus, PSSP involvement and facilitation will be most intense during early and mid-implementation stages as sites plan, trial and refine, and will decrease as delivery practices stabilize and become routine. The facilitators will monitor program progress in a task log based on Meyers⁵⁹. Achievement of key implementation milestones will be reported and areas flagged where more support may be needed. Correspondingly, involvement of ECHO will increase over time to support NAVIGATE as part of routine practice and this will also be monitored. The stages of our implementation process include:

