Stage 1. Exploration (to assess site capacity and need, build engagement): This stage is key to successful practice change. As EPION members who are committed to this project, there is already considerable engagement among participating sites. Additionally, having participated in the prior sector surveys and fidelity reviews, NAVIGATE was identified as a strategy to improve upon current practice at each site. In this stage the CAMH NAVIGATE experts, PSSP facilitators, and ECHO team will meet with each site to explain NAVIGATE, learn about their current staffing and service delivery processes, and discuss how NAVIGATE could be integrated into their practice. Staff will complete a site readiness assessment survey and a program fidelity review will be conducted to learn more about site capacities and needs for NAVIGATE implementation.

Stage 2. Installation (to create structures/build capacity for implementation): Intensive staff training over several days will include a didactic component, role playing, and discussions with individual sites to best fit NAVIGATE with each site’s current processes. The training will initially require three days at the coordinating site (CAMH, Slight Centre), co-led by NAVIGATE trainers from the RAISE study, or equivalent training. Regular site visits from PSSP facilitators and CAMH Slight Centre content experts will occur to develop the local implementation plan working with each site lead to prepare staff. Preparation for practice change will include discussions of: role allocation among staff (i.e. IRT vs. SEE vs. family psychoeducation program); whether the program needs to partner with an external service to deliver some elements (particularly the smaller sites); any changes to current patient flow required to deliver NAVIGATE (the care path); how contact and progress note data will be collected and used in meetings to review progress in NAVIGATE delivery; and how to prepare for ECHO sessions (topics and cases). The ECHO team will also work with each site to ensure set-up and ongoing functioning of infrastructure for live video-conferencing.

Stage 3. Initial implementation (trialing and refining) and Evaluation of Implementation Quality: During this stage, each site will begin NAVIGATE delivery and use feedback from various sources, including ECHO

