ii.b.) Contextual Factors (ADAPTABILITY & SCALABILITY): The Consolidated Framework for Implementation Research (CFIR)⁶² will be used to systematically assess contextual factors that are associated with effective implementation. The CFIR offers a comprehensive menu of constructs from published frameworks that influence implementation. The constructs are organized within five major domains: intervention characteristics (e.g., complexity, relative advantage); outer setting (e.g., external policy, patient needs); inner setting (e.g., resources, fit, leadership); staff characteristics (e.g., knowledge, beliefs); and implementation process (e.g., facilitation, planning, coaching). Similar to the Damschroder approach^{64,65}, the CFIR will be used to develop a semi-structured interview to guide data collection. Interviews will be conducted with stakeholders at each site (EPI staff, organization leaders) at the end of the active implementation, recorded, and transcribed. The CFIR will provide the organizing framework for qualitative data coding and analysis, while being open to new, emergent themes. At each analysis stage, coding and development of themes will be conducted by multiple coders, with consensus achieved through discussion and deliberation. We will develop summary statements of relevant constructs for each site. In combination with fidelity results, we will look for patterns within and across sites related in implementation facilitators and challenges. Qualitative analysis will be supported with NVivo software.

iii) SUSTAINABILITY: ECHO coaching is expected to build staff competencies in delivery of NAVIGATE and to support longer-term sustainability of high quality NAVIGATE delivery. Our evaluation of ECHO will adhere to an established evaluation framework led previously by the ECHO team, building on continuing education program evaluation^{66,67}. At each study site we will assess staff participation (engagement and retention); staff satisfaction with ECHO support; and perceived changes in competence to perform NAVIGATE. Staff attendance during ECHO sessions will indicate ECHO engagement and

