retention. Competency assessment questionnaires will be administered to staff prior to participation in ECHO sessions and at the conclusion of each ECHO cycle to assess changes in attitudes, knowledge and self-efficacy (self-reported competence) in delivering NAVIGATE components. These questionnaires will be based on pre-existing evaluation questionnaires used for ECHO-ONMH³⁹.

ECHO pre-post questionnaires will assess participants before and after each ECHO cycle. The staff knowledge and skills questionnaire is based on survey design literature and Bandura's self-efficacy question framework. The questionnaire has been previously used to assess ECHO Ontario Mental Health programs and will be adapted to assess participants' confidence and self-reported capability in delivering NAVIGATE components. Question domains will include Likert scales assessing self-reported knowledge and skill domains specific to the NAVIGATE model. Self-efficacy questions will focus on key competency domains of NAVIGATE and assess confidence in delivering these components in their local settings.

Site implementation of NAVIGATE into practice will be assessed at the CFIR interviews on factors associated with successful implementation will explore the role of ECHO as a support for sustainability, including the formation of a community of practice. Additionally the readiness assessment⁶⁸ will assess site capacity at the end of the study to continue NAVIGATE. Site readiness scores will be combined with CFIR and fidelity results for a qualitative examination of patterns within and across sites related in implementation facilitators and challenges.

Implementation evaluation measures and timeline						
Implementation stage		Explore (stage 1)	Install (stage 2)	Initial imp. (stage 3)	Full implementation & sustainability (stage 4)	
Measurement domain	Measure	Capacity & needs Ax	Plan & prepare	Trial & refine	Stabiliz e practic e	Practice is routine
		Months 1-3	Months 4-6	Months 7-12	Months 13-24	Months 25-42
Implementation process						
Implementation log (milestones, risk, action)	QIF (adapted)	•	•	•	•	•
ECHO implementation (clinical coaching)	Post-session questionnaires, surveys, and/or phone calls	•	•	•	•	•
Implementation outcomes (organizational capacity)						
Staff survey (readiness to implement)	RMT adapted	•			•	•
Fidelity to EPI model	FEPS-FS	•			•	•
Fidelity to NAVIGATE (clinician report)	Clinician contact form		•	•	•	•
Fidelity to NAVIGATE (client report)	SURF		•	•	•	•

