Staff interview (value and feasibility)*	CFIR adapted					•
Implementation outcomes (staff capacity)						
Staff survey (knowledge and skills)	ECHO survey	•			•	•

* includes perceptions of ECHO support

System Level Outcomes + Analytic Plan (Objective 2):

Data Sources: The primary data collected for patients of the NAVIGATE protocol will be linked deterministically to data sources held at the Institute for Clinical Evaluative Sciences (ICES) via their unique health card number. The patient-level outcomes are enhanced by routine system-level outcome measurement and the capacity to compare outcomes among NAVIGATE subjects with two control populations: 1) FEP subjects in Ontario who are not part of the NAVIGATE trial but are receiving EPI services; and 2) FEP patients with no EPI contact. Only NAVIGATE patients who have consented will have their program-level data linked to ICES. The following ICES data sources will be used: the Ontario Health Insurance Plan (OHIP) which covers data for physician billings; the Canadian Institute for Health Information Discharge Abstract Database (CIHI-DAD) which covers all hospitalizations; the Ontario Mental Health Reporting System (OMHRS), covering adult mental health hospitalizations; the National Ambulatory Care Reporting System (NACRS) for emergency department (ED) visits; the Ontario Drug Benefits (ODB) which provides information on all prescriptions covered by the ODB (based on financial need for those under 65 years of age and universally for young people up to age 25); and the Registered Persons Database (RPDB) containing information on patient demographics and deaths. The Ontario Community Assessment of Need (OCAN) database captures all first episode patients attached to EPI programs in Ontario. OCAN will be used to develop a control population of FEP patients who are attached to non-NAVIGATE EPI programs. Statistics Canada estimates will be used to derive neighbourhood income and rurality. These data sources can be linked via the encrypted health card number such that all the information is available for each individual, and de-identified.

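### The text and the timeline table give different schedules for the ECHO staff competence survey, and on the table's schedule the first change cannot separate ECHO from the NAVIGATE training

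*Combined protocol and SAP*

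**What the plan says.** Section 4 (NAVIGATE Implementation Approach) assesses sustainability through uptake of ECHO. The rationale is that "ECHO coaching is expected to build staff competencies in delivery of NAVIGATE and to support longer-term sustainability". Three things are measured at each site: staff participation, satisfaction with ECHO support, and perceived change in competence.

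The text gives the survey timing twice. First: "Competency assessment questionnaires will be administered to staff prior to participation in ECHO sessions and at the conclusion of each ECHO cycle". Then: "ECHO pre-post questionnaires will assess participants before and after each ECHO cycle". The questions concern knowledge, skill and confidence in the NAVIGATE components. The length, number and dates of ECHO cycles are not stated.

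The table of implementation evaluation measures and timeline has a row "Staff survey (knowledge and skills"), with the ECHO survey as its instrument. It is marked in months 1-3, 13-24 and 25-42 and blank in months 4-6 and 7-12. The ECHO coaching row of the same table is marked in all five windows.

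The NAVIGATE training belongs to Stage 2: "Stage 2. Installation (to create structures/build capacity for implementation): Intensive staff training over several days will include a didactic component, role playing". The table heads Stage 2 as months 4-6. The narrative is looser: "we expect that installation (see below) will occur across the first six months, that trialing and refining will occur during months 7-12".

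**The concern.** A before-and-after measure of staff competence can bear on ECHO only if its starting point comes after the other large source of learning, the initial NAVIGATE training. On the table's schedule the starting point is in the exploration stage and the next survey is in months 13-24. The training, the most intensive period of facilitation and the first months of delivery all lie in between. The survey asks about the skills that the training teaches, so staff could report a gain over that interval even if ECHO added nothing.

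The text does not rule this out. A survey in months 1-3 also counts as being before ECHO participation, and nothing requires a baseline after the training. Of the three listed ECHO measures, this is the only one that addresses competence. At stake is whether a reported gain can be linked to ECHO rather than to the training.

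**Working it through.** No sample size, effect size or test is stated for this survey, so there is no plan figure to reproduce. The check compares the two schedules and does arithmetic on the month windows.

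**Step 1. Text against table.**

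| Window | Stage | ECHO coaching row | ECHO survey row |
|---|---|---|---|
| Months 1-3 | 1 | marked | marked |
| Months 4-6 | 2 (training) | marked | blank |
| Months 7-12 | 3 | marked | blank |
| Months 13-24 | 4 | marked | marked |
| Months 25-42 | 4 | marked | marked |

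The text asks for surveys around every cycle. The table has none in months 4-12, a span of 12 − 4 + 1 = 9 months, although it marks ECHO activity there. The Stage 3 narrative also has sites using feedback from ECHO in that period.

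The blanks do not look accidental. Other rows (the implementation log, the clinician contact form and the SURF) are marked in months 4-12. The ECHO survey row has the same marks as the FEPS-FS row, which the text says is done at three time points.

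**Step 2. First change on the table's schedule (months 1-3 to months 13-24).**
- Shortest gap: 13 − 3 = 10 months.
- Longest gap: 24 − 1 = 23 months.
- By the table's headings, all of Stage 2 (months 4-6) and Stage 3 (months 7-12) lies inside this gap with no survey. The change therefore includes the training, the facilitation, early delivery and ECHO.

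**Step 3. Second change (months 13-24 to months 25-42).**
- Shortest gap: 25 − 24 = 1 month.
- Longest gap: 42 − 13 = 29 months.
- This lies after the Stage 2 training and does not include it. Its starting survey is taken once ECHO is under way, so it has no pre-ECHO baseline.

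**Step 4. When do ECHO sessions start?** The documents point both ways. In Stage 2, sites are still discussing "how to prepare for ECHO sessions (topics and cases"), which suggests a start after training. The table, however, marks ECHO post-session measures already in months 1-3. No start month is given.
- If sessions start after training and the text is followed, a survey just before the first cycle would come after the training.
- If sessions start in months 1-3, a survey taken before the first session precedes the training under the text as well.

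On neither schedule is a survey between training and ECHO guaranteed.

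**The case against.** The strongest reply is that the text already states a workable rule. If surveys are done before and after each cycle and ECHO begins after installation, the first survey follows the training and most of the problem disappears. That is correct, but it means the table has to be changed, and the plan does not say which schedule governs.

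Several stronger readings are tempting, and the documents do not support them:

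- **The table's interval is not an ECHO cycle.** This cannot be shown, because no cycle length or date is given. Three marks could fit two long cycles, or the table could be a summary by stage. A long first cycle would still contain the training.
- **The whole gain would be credited to ECHO.** No scoring or attribution rule is stated. The table files the survey under staff capacity, for which a pre-training baseline is reasonable.
- **Both changes are affected.** Only the first spans the Stage 2 training. For a sustainability question the second is arguably the more relevant one.
- **Staff start with almost no competence, and most of the gain is due to training.** The background section says sites had already met NAVIGATE in didactic sessions and conferences. No effect sizes are given, so any percentage would only restate the assumptions behind it.
- **A recommendation on ECHO would rest on this score.** Sustainability also draws on attendance, satisfaction, interviews that explore ECHO's role, end-of-study readiness, and a fidelity review at study end. ECHO has no hypothesis or decision rule of its own.

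It is also fair to object that a post-training baseline does not isolate ECHO. Facilitation and practice continue alongside it, and there is no control group. That objection stands and limits what the fix can claim.

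**Conclusion.** The point holds in limited form, and its severity is minor. The text and the table give survey schedules that are not reconciled, and ECHO cycle dates are missing. If the table is followed, one of the two available changes (months 1-3 to 13-24) contains the NAVIGATE training and cannot be read as a change due to ECHO. The other avoids the training but lacks a pre-ECHO starting point.

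This rests on two assumptions: that staff would field the survey as the table shows, and that the training falls in months 4-6 as the table heads Stage 2. The narrative places installation only within the first six months, so the order of the first survey and the training is likely rather than certain. The size of the training contribution cannot be derived from the documents. No primary outcome or sample size is affected.

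**What to change.** 1. State the start and end dates of each ECHO cycle, and correct the table so that a survey is marked at the end of each one, including in months 7-12.
2. Add one send-out of the same questionnaire right after the Stage 2 training. If ECHO sessions start after training, place it before each person's first session.
3. Keep the months 1-3 survey as a separate pre-training measure.
4. Report two changes, each paired within person: pre-training to post-training, and post-training onward. Describe the second as change during ECHO together with facilitation and practice, not as an isolated ECHO effect.

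The cost is a correction to the table, one extra send-out of a questionnaire already in use, and slightly more survey burden for staff. If the table was meant to govern, the end-of-cycle surveys are also additional to it, though the text already calls for them. The post-training send-out should be settled before the training takes place, because that measurement cannot be recovered later.
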